## Background

Despite the growing adoption of continuous glucose monitoring (CGM) and advances in insulin therapies, overnight low glucose is still a common problem for people living with type 1 diabetes (T1D). Nocturnal hypoglycemia, which accounts for 55% of level-two hypoglycemia events (glucose < 54 mg/dL) in people with type 1 diabetes (T1D) and 75% of level-two hypoglycemia events in children with T1D,[16]–[18] is particularly dangerous because people are unlikely to recognize symptoms while sleeping and are also less likely to awaken in response to hypoglycemia alarms from continuous glucose monitors (CGMs).[1], [2] In addition to the serious short-term effects of nocturnal hypoglycemia episodes, untreated nocturnal hypoglycemia can further impair the physiological counter-regulatory system and contribute to hypoglycemia unawareness.[3]–[5] Hypoglycemia unawareness may eventually result in recurrent asymptomatic hypoglycemia[19] and in some cases the dead in bed syndrome due to prolonged exposure to extremely low blood glucose levels during sleep.[20]

Advanced insulin therapies such as continuous subcutaneous insulin infusion (CSII) with insulin pumps and closed-loop systems are now available for managing glucose. However, most people with type 1 diabetes continue to use multiple daily injections (MDI).[21], [22] A recent study showed that MDI users spent more time with sensor glucose <54 mg/dL and experience more hypoglycemia episodes overnight than pump or closed-loop users.[22] Therefore, there is a need for effective interventions that help people with T1D on MDI to prevent nocturnal hypoglycemia.

Our group at the Oregon Health & Science University (OHSU) developed and evaluated a smartphone-based decision support app called DailyDose that combines CGM data and insulin data to provide comprehensive decision support for people with T1D on MDI. DailyDose provides on-demand insulin dosing recommendations, suggestions for glucose management around exercise, and hypoglycemia and hyperglycemia alarms.[6], [7] These features will not be

used in this study. A new feature of DailyDose, which will be evaluated in this study, is a module for prevention of low glucose overnight that provides a personalized bedtime *smart snack* recommendation based on the minimum overnight glucose level predicted by an advanced artificial intelligence (AI)-based model.

### **Primary Objective**

To evaluate the benefit of an AI-based *smart snack* intervention (AI prediction model + personalized bedtime snack) in helping people avoid overnight low glucose as measured by the probability of overnight hypoglycemia, versus CGM-based glucose management (control period).

### **Secondary Objectives**

- To measure time from bedtime until first CGM measurement  $<70$  mg/dL if CGM stays below 70 mg/dL for at least 10 minutes
- To evaluate the effect of an AI-based *smart snack* intervention versus CGM-based glucose management (during control period) on glucose control overnight (announced bedtime + 8 hours) and across the full 24-hour/day study duration, as measured by other glycemic outcomes including the following metrics:
  - % time  $< 54$  mg/dL
  - % time  $< 70$  mg/dL
  - % time 70-180 mg/dL
  - % time  $> 180$  mg/dL
  - % time  $> 250$  mg/dL
  - Mean CGM
  - Number of bedtime snacks treatments
- To assess the accuracy of the AI model in predicting overnight low glucose as measured by sensitivity and specificity during the control arm of the study.

### **Study hypothesis**

We hypothesize that a smartphone-based bedtime *smart snack* intervention informed by a low glucose prediction AI model will reduce the probability of overnight hypoglycemia by 50% in people with T1D on MDI therapy compared with traditional CGM-augmented MDI glucose management. The probability of overnight hypoglycemia will be measured as the proportion of nights with nocturnal hypoglycemia episodes during intervention and control periods.

### **Endpoints**

#### **Primary endpoint**

Probability of overnight hypoglycemia. An episode of overnight hypoglycemia is counted if sensor glucose is  $<70$  mg/dL for at least two measurements during an eight-hour period following announced bedtime.

Time frame: The level-one unit of analysis is a single night, and each participant will contribute 27 consecutive nights under each condition.

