## Power analysis

A sample of 20 participants observed for 27 nights in each condition (total number of nights =  $20*27*2 = 1,080$ ) provides >90% power to detect a relative risk (RR) of 0.5 for nights in the intervention period compared to the control period, or >80% power to detect  $RR \leq 0.6$ . This was calculated assuming the risk of 0.09 for overnight hypoglycemia in the intervention period vs 0.18 in the control period (or 0.15 for  $RR=0.6$ ), and an intra-cluster correlation coefficient (ICC) of 0.25. The effect is equivalent to a 50% relative reduction in the likelihood of nocturnal hypoglycemia.

Statistical power for this sample size was calculated by simulating 1,000 datasets with the assumptions above, fitting the mixed effects model, and determining the proportion of those datasets where the p value for the Wald test of the coefficient of the treatment effect was <0.05. Control and intervention proportions were set after reviewing other crossover trials of similar interventions in similar populations.[22], [23] The ICC was determined by drawing samples of

20 individuals/27 nights per person per arm from a combined dataset of nights from the T1D Exercise study T1-Dexi dataset (T1-Dexi is the largest known dataset of physical activity in T1D, a joint effort by The Leona M. and Harry B. Helmsley Charitable Trust, Jaeb Center for Health Research, and the T1-Dexi study group) and a dataset provided to our group at OHSU by Glooko Inc (Mountain View, CA, USA), then calculating the ICC in an unconditional model. An ICC of 0.25 is just below the mean for ICCs calculated over 500 resamples (ICCMEAN = 0.27). In the resampled source data, 85% of participants experienced hypoglycemia on at least one of the 27 sampled nights.

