## Protocol summary

Participants will be randomized to either first use CGM only to manage glucose for four weeks (control arm, usual care) followed by four weeks of DailyDose App + bedtime *smart snack* intervention (intervention arm), or vice-versa. There will be a one- to four week washout period between arms. See Figure 1 for a diagram of the study flow.

During the control arm, participants will wear CGM and will manage their glucose as usual (current care). Participants will be asked to wear a smart watch overnight to collect sleep metrics, weigh themselves weekly in the morning before eating, and answer a one-item sleep quality scale survey weekly. We will collect CGM measurements during the control arm for evaluation of effect of intervention and assessment of the accuracy of low glucose prediction.

During the *smart snack* intervention arm, participants will use the DailyDose app when they are getting ready for bed. An AI-based model in DailyDose will predict the likelihood of overnight low glucose at bedtime every night and will recommend a personalized snack to help avoid nocturnal hypoglycemia. The nutritional content of the snack (carbohydrate, protein, fat, etc.) will be dependent on the predicted overnight minimum glucose and the predicted time of the minimum overnight glucose level. During this arm, participants will also be asked to wear a smart watch overnight, weigh themselves weekly, and answer a one-item sleep quality scale survey weekly.

[figure not shown]

Figure 1. Study flow diagram

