### **DailyDose + *smart snack* intervention arm (4 weeks)**

There will be a visit at the start of the intervention arm that will be held at OHSU's Biomedical Engineering Artificial Intelligence for Medical Systems (AIMS) Laboratory, the Harold Schnitzer Diabetes Health Center, or virtually using WebEx. A urine pregnancy test might be required for individuals of childbearing potential if the last pregnancy test was more than 7 days prior. This test must be negative before further participation is allowed. During this session, participants will go through the onboarding process with the DailyDose app. This process will occur with the study staff and involve:

- Training on using the Dexcom G6 CGM within the DailyDose app
- Setting up low and high blood glucose CGM-based alerts

- Setting up bedtime for running nocturnal low glucose prediction and receiving bedtime snack recommendation when applicable
- Review *smart snack* options that will be recommended by DailyDose and provided to participants during the intervention period (study protocol, Table 1) as well as present accessible snack alternatives (e.g., those already documented in the study protocol Table 2), in case participants has any allergies or food aversion related to DailyDose *smart snack* options. The study staff will also provide a card with bedtime snack options and replacements so that participants can easily find adequate alternatives to the snacks recommended by DailyDose (study protocol, Appendix F).
- Training on usage of the DailyDose app including how to setup alerts, predict likelihood of nocturnal low glucose, accept/decline *smart snack* recommendations, and use of the insights tab / settings / logbook features
- Training on usage of the Apple Watch

DailyDose has glucose alerts for safety. The Dexcom G6 CGM alerts in DailyDose will be set at 70 mg/dL and 250 mg/dL with user able to adjust. For participants with history of severe hypoglycemia requiring third party assistance, low glucose alerts will be conservatively set to 85 mg/dL. There is a very low glucose alert (glucose <55 mg/dL) that cannot be adjusted.

This visit will take approximately 2-3 hours, depending on the subject's experience.

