### **Missing data**

Participants who contribute at least 14 nights plus 24 hours following bedtime in at least one of the study conditions will be included in the analysis. Missing sensed glucose values will be interpolated for up to 30 min segments. Longer periods of missing data will be omitted. If missing data represent >10% of observation time (which will be truncated if a participant leaves the study early), we will examine distributions of other variables in the dataset to see if they differ between those with high/low levels of missingness. We will consider methods to reduce bias in the estimate of treatment effect such as including covariates in the main outcomes model.

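### The overnight window starts at an announced bedtime that neither arm defines, so app use could decide which intervention nights are scored

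*Combined protocol and SAP*

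**What the plan says.** The Primary endpoint section counts an episode when sensor glucose is below 70 mg/dL for at least two measurements "during an eight-hour period following announced bedtime". The overnight metrics under Secondary Objectives and Secondary Endpoints use the same eight-hour window. No section says who announces bedtime, how it is recorded, or how a night without an announcement is handled.

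The intended denominator is every night. The Primary endpoint section states that "each participant will contribute 27 consecutive nights under each condition", and the Study hypothesis says the probability is "measured as the proportion of nights with nocturnal hypoglycemia episodes during intervention and control periods".

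For the intervention arm, the Protocol summary says "participants will use the DailyDose app when they are getting ready for bed". The intervention-arm section also lists, at onboarding, "Setting up bedtime for running nocturnal low glucose prediction and receiving bedtime snack recommendation when applicable". The control-arm section describes CGM and watch wear, but no bedtime announcement.

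The Missing data section gives the rule for entering the analysis: "Participants who contribute at least 14 nights plus 24 hours following bedtime in at least one of the study conditions will be included in the". The remaining rules there concern gaps in the glucose trace. The compliance analysis uses recommendation accepted or rejected, with no category for a night when the app was not opened.

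**The concern.** If the announcement is made by using DailyDose, then using the intervention also creates the scoring window. A participant who forgets or skips the app still has a CGM trace for that night, but nothing in the text says when the eight hours begin. An analyst would have to choose whether to drop the night, count it as free of hypoglycemia, or supply a start time.

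Under the first two choices, whether an intervention night can contribute an event depends on behaviour after randomisation, in an open-label trial, while the stated intent is 27 consecutive nights per condition. The existing safeguards do not clearly catch this. The CGM may be complete, so the missing-glucose rules need not apply. The extra study time described under Study Completion session is for supply, technical and scheduling problems, not for forgetting the app.

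**Working it through.** **Inputs from the plan (Power analysis).** "A sample of 20 participants observed for 27 nights in each condition", "assuming the risk of 0.09 for overnight hypoglycemia in the intervention period vs 0.18 in the control period", and an ICC of 0.25. That is 20 × 27 = 540 nights per condition.

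**Assumptions, because the documents give no figure.** The share q of intervention nights without app use is 10, 20 or 30% (54, 108 or 162 of 540 nights). Risk on non-use nights is varied below. The ICC is taken on the latent logistic scale and the test as two-sided, since the plan states neither. All control nights are taken as scored.

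**1. The plan's own figure.** The method was 1,000 simulated datasets, a logistic mixed model with treatment, sequence, period and a random participant intercept, and a Wald test at 0.05. With the rates read as marginal, power is 99.4% for 0.18 vs 0.09 and 88.5% for 0.15 vs 0.09. Read as conditional, it is 98.9% and 87.0%. The stated >90% and >80% are reproduced.

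**2. Effect of the handling rule when the app works on nights it is used.** Risk is 0.09 on used nights and, by assumption, 0.18 on non-use nights.

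- All nights kept: RR = [0.09(1 − q) + 0.18q] / 0.18 = 0.5 + 0.5q
- Non-use nights dropped: RR = 0.09 / 0.18 = 0.50
- Non-use nights scored as no event: RR = 0.09(1 − q) / 0.18 = 0.5(1 − q)

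| q | All nights | Dropped | No event |
|---|---|---|---|
| 10% | 0.55 | 0.50 | 0.45 |
| 20% | 0.60 | 0.50 | 0.40 |
| 30% | 0.65 | 0.50 | 0.35 |

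At q = 20%, a 40% reduction over all nights would be reported as 50% (dropped) or 60% (no event).

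**3. Direction of the bias.** Write u for the risk on used nights and s for the risk on skipped nights. The all-night RR minus the dropped-nights RR is q(s − u) / 0.18. Dropping therefore flatters the intervention when s > u and works against it when s < u. Scoring as no event removes any events on skipped nights while keeping those nights in the denominator, so it can only lower the intervention rate.

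**4. No true effect (600 simulated trials per row; Monte Carlo error up to about 2 points).**

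- No event, risk 0.18 on every night: RR = 1 − q = 0.90, 0.80, 0.70. The false-positive rate is about 13%, 40% and 70%.
- Dropped, skipped nights at average risk: RR about 1, rejection about 2 to 6%.
- Dropped, q = 20%, overall risk held at 0.18, so u = (0.18 − 0.2s) / 0.8:

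| s | u | RR = u / 0.18 | Rejection rate |
|---|---|---|---|
| 0.12 | 0.195 | 1.08 | about 12.5%, nearly all against the intervention |
| 0.27 | 0.1575 | 0.875 | about 18% |
| 0.36 | 0.135 | 0.75 | about 53% |

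**5. Power if every night is scored.** Under the step 2 assumptions, all-night power is about 98%, 94% and 87% at q = 10, 20 and 30%.

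**The case against.** The strongest reply is that the documents never say a non-use night is dropped or scored as no event. A reader might infer that the effect is judged only on nights the app was used. That goes further than the text. It would follow only under a drop rule, because a night scored as no event stays in the denominator. It also conflicts with the stated intent to count all nights of each period. The bedtime set up at onboarding, together with a model described as predicting every night, fits a preset nightly bedtime that needs no app opening; in that case the problem disappears. Moreover, if announcing meant opening DailyDose, no control night could be scored, so that is probably not the intended meaning. All of this stands. What remains is that no section makes the preset bedtime the scoring origin, and none names a control-arm source.

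A reader might also take the 14-night rule to mean that up to 13 of 27 intervention nights can be lost. It does not set that limit: it asks for 14 nights in at least one condition, so it fixes no minimum for the intervention arm when control nights suffice. In the other direction, the Withdrawal Criteria require withdrawal for substantial and repeated non-compliance, which limits extreme cases. App predictions reach a study server and staff contact participants weekly, so non-use could be noticed.

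Nor do the documents support saying that dropping nights must inflate the effect. That depends on the risk on skipped nights, which is not given. Finally, the objective speaks of the benefit of the intervention and the Study Type section of efficacy. The case for scoring all nights rests on the stated denominator, not on an objective of offering the app.

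**Conclusion.** The concern holds as a conditional gap and is worth closing. The scoring window has no defined source in either arm, and no rule covers a night with CGM but no announced bedtime. If the onboarding bedtime serves as the announcement every night, the bias from non-use is zero. If not, and non-use nights carry control risk, the reported RR differs from the all-night RR by 0.05 to 0.15 when they are dropped and by 0.10 to 0.30 when they are scored as no event, for an assumed non-use share of 10 to 30%. Dropping can bias in either direction; scoring as no event favours the intervention and can produce substantial false-positive rates. The non-use share and the risk on skipped nights are assumptions. The stated power is not in dispute.

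**What to change.** In Primary endpoint, Secondary Endpoints and Missing data, state that every night of the assigned period with adequate CGM is scored in its assigned condition, whether or not the app was opened, and define adequate.

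Start the eight-hour window from one pre-specified source applied the same way to all nights in both arms. Options are a usual bedtime recorded at the start of each period; Apple Watch sleep onset with that bedtime as back-up; or the 10 PM to 6 AM window already used in the Inclusion criteria. Do not use a fallback only on non-use nights: sleep onset normally follows getting ready for bed, so that would make the time origin depend on adherence.

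Report non-use nights per participant, and give the app-used-nights result as a secondary analysis.

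The cost is wording and a derivation step. CGM and watch data are already collected in both arms; a recorded usual bedtime would add one item at the start of each period. The downsides are a less exact window start, some dependence on watch wear if sleep onset is chosen, and a possibly smaller estimated effect.

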#### **Secondary Endpoints**

- Time to the first low-glucose event (<70 mg/dL). Time until first CGM measurement <70 mg/dL when CGM remains < 70 mg/dL for at least 10 minutes
- Percentage of time in clinically relevant glucose ranges:
  - % time < 54 mg/dL
  - % time < 70 mg/dL
  - % time 70-180 mg/dL
  - % time > 180 mg/dL
  - % time >250 mg/dL

Time frames: overnight (announced bedtime + eight hours) and across the full 24-hour/day study duration

- Mean glucose in mg/dL

Time frames: overnight (announced bedtime + eight hours) and across the full 24-hour/day study duration

- Accuracy of overnight low glucose prediction as measured by sensitivity and specificity as measured during the control arm of the study
- Change in weight from start to end of intervention period, start to end of control period

## Study Type

This is a single-center, open-label, crossover trial with two arms and two periods (2x2) and one-week washout period. The study is designed to evaluate the efficacy of an AI-based bedtime *smart snack* intervention in reducing nocturnal low glucose in people living with T1D on MDI therapy compared with traditional CGM-augmented MDI therapy as the control.

## Study population

The study population will be adults with type 1 diabetes, aged 18 or older. Younger participants are excluded as it is appropriate to assess efficacy of proposed intervention first in the adult population. Twenty participants will be recruited to participate in this study.

## Power analysis

A sample of 20 participants observed for 27 nights in each condition (total number of nights =  $20*27*2 = 1,080$ ) provides >90% power to detect a relative risk (RR) of 0.5 for nights in the intervention period compared to the control period, or >80% power to detect  $RR \leq 0.6$ . This was calculated assuming the risk of 0.09 for overnight hypoglycemia in the intervention period vs 0.18 in the control period (or 0.15 for  $RR=0.6$ ), and an intra-cluster correlation coefficient (ICC) of 0.25. The effect is equivalent to a 50% relative reduction in the likelihood of nocturnal hypoglycemia.

Statistical power for this sample size was calculated by simulating 1,000 datasets with the assumptions above, fitting the mixed effects model, and determining the proportion of those datasets where the p value for the Wald test of the coefficient of the treatment effect was <0.05. Control and intervention proportions were set after reviewing other crossover trials of similar interventions in similar populations.[22], [23] The ICC was determined by drawing samples of

20 individuals/27 nights per person per arm from a combined dataset of nights from the T1D Exercise study T1-Dexi dataset (T1-Dexi is the largest known dataset of physical activity in T1D, a joint effort by The Leona M. and Harry B. Helmsley Charitable Trust, Jaeb Center for Health Research, and the T1-Dexi study group) and a dataset provided to our group at OHSU by Glooko Inc (Mountain View, CA, USA), then calculating the ICC in an unconditional model. An ICC of 0.25 is just below the mean for ICCs calculated over 500 resamples (ICCMEAN = 0.27). In the resampled source data, 85% of participants experienced hypoglycemia on at least one of the 27 sampled nights.

## Protocol summary

Participants will be randomized to either first use CGM only to manage glucose for four weeks (control arm, usual care) followed by four weeks of DailyDose App + bedtime *smart snack* intervention (intervention arm), or vice-versa. There will be a one- to four week washout period between arms. See Figure 1 for a diagram of the study flow.

During the control arm, participants will wear CGM and will manage their glucose as usual (current care). Participants will be asked to wear a smart watch overnight to collect sleep metrics, weigh themselves weekly in the morning before eating, and answer a one-item sleep quality scale survey weekly. We will collect CGM measurements during the control arm for evaluation of effect of intervention and assessment of the accuracy of low glucose prediction.

During the *smart snack* intervention arm, participants will use the DailyDose app when they are getting ready for bed. An AI-based model in DailyDose will predict the likelihood of overnight low glucose at bedtime every night and will recommend a personalized snack to help avoid nocturnal hypoglycemia. The nutritional content of the snack (carbohydrate, protein, fat, etc.) will be dependent on the predicted overnight minimum glucose and the predicted time of the minimum overnight glucose level. During this arm, participants will also be asked to wear a smart watch overnight, weigh themselves weekly, and answer a one-item sleep quality scale survey weekly.

[figure not shown]

Figure 1. Study flow diagram

